Treatment of first-time traumatic anterior shoulder dislocation

(UK.TASH-D Study)

Study Protocol

**National Institute for
Health Research**

Full Study Protocol

NIHR HTA Commissioned Study: Treatment of first-time traumatic anterior shoulder dislocation (UK.TASH-D Study).

Version Control Table

Version	Date	Amendments
Version 1	December 2015	
Version 2	February 2016	Due to changes in CPRD services being offered in 2016 a GP questionnaire will now be used in Stage 1 of this study. See amendment section at end. Rather than obtain 100 sets of notes and use the validation algorithm in Appendix H, GP's will use a GP Questionnaire (Attached in Appendix I). This questionnaire follows the validation algorithm in Appendix H and has extra questions to ensure maximum data and information is obtained for subsequent analysis. CPRD quote a high 80% return rate with such questionnaires.

A. Lay Summary (Max. 200 words)

Traumatic anterior shoulder dislocation (TASD) is when the top end of the arm bone at the shoulder is forced out of the shoulder socket frontwards. This happens after injuries and is common in younger patients. It is very painful and the shoulder often stays dislocated until it is 'put back' in hospital. The joint can remain 'unstable' with more dislocations. The two main ways of treating this problem are physiotherapy and surgery. We still don't know the best choice and so it is important to know if surgery or physiotherapy after one dislocation is worthwhile in preventing further problems.

We should be able to answer this question using information that is already available within the NHS in two computerised systems called CPRD and HES. We have put together a research team with expertise in shoulder dislocation and expertise in studying these two databases. We plan to first check the coding of shoulder dislocations in the CPRD database by performing an initial assessment phase. If this is successful it means we can answer the question and we will then do a full analysis of the databases. We will then publicise our results widely so patients get the correct and optimum treatment.

B. Technical Summary (Max. 200 words)

Aims: To study the association between surgical treatment to no surgery and recurrence rates following first time TASD in young adults; and identify predictors of recurrent dislocations stratified by treatment.

Data sources: Clinical Practice Research Datalink (CPRD) linked to Hospital Episode Statistics (HES).

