Population: 10,449 patients aged 16-35 years in CPRD with TASD and two years follow up.

WP1: Internal and external validation of shoulder dislocation coding and treatments within a routinely collected dataset (CPRD).

WP2: Propensity score-matched cohort study using linked CPRD and HES. All events and outcomes will be collected using a pre-agreed list of READ CODES (CPRD) and OPCS 4.7 CODES (HES).

Exclusions: Surgery after more than one dislocation; instability treated with a rotator cuff repair or fracture surgery.

Intervention: Surgical repair within 6 months of first time T ASD.

Control: non-surgical intervention.

Outcomes: Rate of re-dislocation, identified by codes in CPRD for 2 years after either treatment.

Sample size: 3065 with 656 expected total number of re-dislocations (90% power, 5% significance).

Statistical analysis: Propensity scores, Cox regression modelling and Rosenbaum bounds sensitivity analysis for *Surgical versus non-surgical intervention on re-dislocation*. Multiple imputation methods, survival models and fractional polynomials for *Predictors of recurrent dislocations*.

C. Objectives, Specific Aims and Rationale

Aim 1. To study the association between surgical treatment (compared to no surgery) and recurrence rates following a first episode of traumatic anterior shoulder dislocation (T ASD) amongst young adults. **Aim 2.** To identify clinical predictors of further recurrent dislocations in young adults with traumatic anterior shoulder dislocation stratified by surgery and no surgery.

Objectives: Following the HTA commissioning brief, we plan to use routinely collected observational datasets (Clinical Practice Research Datalink (CPRD) and Hospital Episodes Statistics (HES)) to answer the research questions above. The size of routinely collected data in UK primary care (CPRD) and secondary care (HES) offers rapid observational data to uncertainties about treatments in an affordable and generalisable manner. We have planned a propensity score-matched cohort study, with the intention to minimise confounding. Propensity score matching is considered one of the best methods available to approximate to any results obtained from randomised controlled trials. To ensure further value for money and to confirm the ability of these datasets to answer this very specific commissioned question, we plan a two stage approach through Work Packages 1 and 2.

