Work Package 1: Data Validation of shoulder dislocation coding and treatments within a routinely collected dataset (CPRD). **Work Package 2:** Population based cohort study using routinely collected datasets (CPRD and HES).

Having run feasibility counts in CPRD and there are 26,534 patients with shoulder dislocations in the database. We expect at least 10,449 to be T ASD in 'young' patients aged 16-35 years of age [7] indicating a very substantial dataset to answer this commissioned call.

D. Background

This project and study has been commissioned by the HTA and as such has already been deemed necessary. We can confirm that since the commissioned call there have been no published systematic reviews, or RCTs that answer the commissioning brief.

Shoulder joint dislocations are the most common joint dislocations seen in hospital A+E departments (8.2-17 cases per 100,000 population/year) with 95% of traumatic glenohumeral dislocations being anterior [15]. Traumatic anterior shoulder instability can carry significant morbidity. Some in the clinical community still quote high re-dislocation rates of 85% [16] and 92% [17] despite more recent larger population studies. A small but highly cited Swedish population study was conducted by Hovelius [18]. This prevalence study was in a random sample of 2092 people aged 18 to 70 years. 1.7% of patients reported a history of dislocation. There was a male to female ratio of 3:1 overall but this ratio varied with age being 9:1 in the 21 to 30 years age group. Hovelius also looked at recurrent dislocation trends

This project was funded by the National Institute for Health Research Health Technology Assessment (project number 14/160/01).

The views and opinions expressed therein are those of the authors and do not necessarily reflect those of the HTA, NIHR, NHS or the Department of Health.

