Main study (WP2): The main study (WP2) will be a population based propensity score-matched cohort study using CPRD and HES collected datasets. The cohort of participants in this study will be young adults (aged 16–35 years) with traumatic anterior shoulder dislocation (T ASD) with at least 2 years data entry in CPRD before the their first shoulder dislocation code and at 2 years follow up from their first dislocation code entry in CPRD. All events and outcomes will be collected using a pre-agreed validated list of READ CODES (CPRD) and OPCS 4.7 CODES (HES). These codes are listed in the appendices and have already been identified. They will be further validated and informed by WP1. The first read code entry in CPRD for shoulder dislocation will be defined as the ‘first dislocation’. These codes will then be routinely linked to patients and to HES.

The ***Intervention group*** will be patients in CPRD with first time T ASD who underwent shoulder stabilisation surgery after their first dislocation (early surgical repair in this NHS context will mean ‘a decision to treat surgically after the first T ASD’ and receiving surgery within 6 months). This means linking HES data to CPRD data in such a way that a HES surgical OPCS 4.7 code is seen to occur after a single first dislocation code in CPRD (without further dislocation codes) before that surgical date. The timelines between first dislocation codes and OPCS 4.7 codes will be recorded. The ***Control group***. While the most desirable control group would be physiotherapy, it is possible that WP1 will reveal that free text notes and referral codes on physiotherapy will be lacking and not reliable. If this is the case then conservative care will be defined as ‘non surgical intervention’ with no linked OPCS 4.7 surgical shoulder codes producing a control cohort of patients whose first time shoulder dislocation has been treated non-operatively. If however free text entries and referral codes for physiotherapy are reliably present in CPRD then conservative care will be physiotherapy identified by physiotherapy referral codes after a first time T ASD code. Any subsequent dislocation codes or OPCS 4.7 surgery code will be recorded.

This project was funded by the National Institute for Health Research Health Technology Assessment (project number 14/160/01).

The views and opinions expressed therein are those of the authors and do not necessarily reflect those of the HTA, NIHR, NHS or the Department of Health.

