The main disadvantage (when compared to RCTs) is the lack of adjustment/matching for unobserved confounders. To measure the impact of such unobserved confounding we will use the Rosenbaum boundaries simulation, where one tests the robustness of the estimated effect by introducing a fake confounder. This simulation exercise measures the strength of association between such confounder and the study exposure and outcome that would account for the observed relationship, therefore giving an estimate of the existing risk of residual confounding explaining the findings.

N. Plan for addressing missing data

The handling of missing data is a key issue in routinely collected data analyses. Although no missing is expected for the study exposure or outcomes, it is indeed likely that data will be missing for some of the confounders in our study.

This project was funded by the National Institute for Health Research Health Technology Assessment (project number 14/160/01).

The views and opinions expressed therein are those of the authors and do not necessarily reflect those of the HTA, NIHR, NHS or the Department of Health.

We will impute missing covariates using multiple imputation by chained equations (MICE) methods. We will use the ICE procedure (Imputation by Chained Equations) in Stata, including all predictor variables in the multiple imputation process, together with the outcome variable and length of follow up time on the log scale as this carries information about missing values of the predictors.

O. Limitations of the study design, data sources and analytical methods

The limitations have all been considered and addressed in the other sections. The study has also been designed deliberately in two stages to ensure data validation is undertaken in stage 1 and that the research questions can be answered before progressing to the full observational study.

P. Patient or user group involvement (if applicable)

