Appendix C

The HES OPCS 4.7 codes that will be used are shown below. These codes have been provided to the lead applicant by the Expert Advisor in Orthopaedics to the Clinical Classifications Service HSCIC (Health and Social Care Information Centre) and Designated Centre for WHO FIC (Family of International Classifications Network). The codes are based on the following procedures “labral repair, stabilisation, capsular shift, Laterjet, bone transfer, SLAP repair and Bankart repair”. For any codes that do not define anatomical site, the following site codes should be present Z81.3 (Glenohumeral Joint) or Z81.4 (Shoulder Joint). The codes in *italics* are usually used for other joints such as the acromio-clavicular joint but we have been informed they are often used for shoulder stabilisation of the glenohumeral joint and will therefore need to be included in the analysis during linkage to CPRD shoulder dislocation codes.

HES OPCS 4.7 CODES.

Operative Description	OPCS 4.7 Codes
Stabilising operations on joint	W77
Repair of capsule of joint for stabilisation of joint NEC	W77.1
Transposition of muscle for stabilisation of joint	W77.2
Blocking operations on joint using prosthesis for stabilisation of joint	W77.3
Blocking operations on joint using bone for stabilisation of joint	W77.4
Periarticular osteotomy for stabilisation of joint	W77.5
Transposition of ligament for stabilisation of joint	W77.7
Other specified stabilising operations on joint	W77.8
Unspecified stabilising operations on joint	W77.9
Prosthetic replacement of ligament	W72
Primary prosthetic replacement of multiple ligaments	W72.1
Prosthetic replacement of multiple ligaments NEC	W72.2
Primary prosthetic replacement of intra-articular ligament	W72.3
Prosthetic replacement of intra-articular ligament NEC	W72.4
Primary prosthetic replacement of extra-articular ligament	W72.5
Prosthetic replacement of extra-articular ligament NEC	W72.6
Other specified prosthetic replacement of ligament	W72.8
Unspecified prosthetic replacement of ligament	W72.9
Other stabilising operations on joint	O27
Extra-articular ligament reconstruction for stabilisation of joint	O27.1

Repair of capsule and anterior and posterior labrum for stabilisation of glenohumeral joint	O27.2
Repair of capsule and anterior labrum for stabilisation of glenohumeral joint	O27.3
Repair of capsule and posterior labrum for stabilisation of glenohumeral joint	O27.4
Other reconstruction of ligament	W74

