APPENDIX D

TABLE OF CPRD DISLOCATION READ CODES

Description	READ Code	Number of clinical events currently recorded in CPRD
Dislocation or subluxation of shoulder	S41.00	51,162
Dislocation of shoulder NOS	S41z.00	11,578
H/O: dislocated shoulder	14G5.00	6,724
Closed reduction of dislocation of shoulder	7K6G300	2,878
Closed traumatic dislocation of shoulder	S410.00	2,240
Recurrent dislocation of shoulder – anterior	N083A00	2,140
Anterior dislocation of shoulder	S410111	1,864
Recurrent joint dislocation, of shoulder region	N083100	1,321
Recurrent subluxation of shoulder – anterior	N083C00	599
Closed traumatic dislocation shoulder jnt. Anterior (sub-coracoid)	S410100	439
Closed traumatic dislocation shoulder joint, unspecified	S410000	439
Closed traumatic subluxation, shoulder	S412.00	288

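### Re-dislocation and the single-dislocation check before surgery rest on GP codes alone; the linked hospital code list cannot identify a dislocation, so hospital events the GP did not code are missed

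*Protocol*

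**What the plan says.** - **Outcome.** Protocol section B: "Rate of re-dislocation, identified by codes in CPRD for 2 years after either treatment".
- **Surgical group.** Sections F and J require that "a HES surgical OPCS 4.7 code is seen to occur after a single first dislocation code in CPRD (without further dislocation codes") before the operation date. HES supplies the operation; CPRD supplies the dislocation count. Section I excludes surgery after more than one dislocation.
- **General statement on sources.** Section B: "All events and outcomes will be collected using a pre-agreed list of READ CODES (CPRD) and OPCS 4.7 CODES (HES"). Section F repeats this for the main study.
- **Code lists.** Appendix C bases the HES list on "labral repair, stabilisation, capsular shift, Laterjet, bone transfer, SLAP repair and Bankart repair". The only list of dislocation codes is Appendix D, "TABLE OF CPRD DISLOCATION READ CODES", which includes a Read code for closed reduction of a dislocated shoulder.
- **Linkage.** Section I makes CPRD-HES linkage an inclusion criterion.
- **Where dislocations are treated.** Section A says "the shoulder often stays dislocated until it is" put back in hospital. Section D: "Shoulder joint dislocations are the most common joint dislocations seen in hospital A+E departments".
- **Validation.** Section F stops the study if first or recurrent dislocation coding is poor, and quantifies the go decision as a positive predictive value of at least 75%. Questionnaire items 6b and 6c in Appendix I ask whether repeat codes are true new episodes and whether there were recurrences that were not coded.

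**The concern.** The general statement on sources suggests that hospital data contribute to dislocation events. With the lists as written they cannot, because no HES code in Appendix C identifies a dislocation or its reduction. The study accepts closed reduction as a dislocation marker in GP data but does not look for it in the hospital data it already links.

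There are two consequences. First, the primary endpoint misses re-dislocations that were recorded in hospital and not coded by the GP. Second, a patient operated on after an uncoded second dislocation passes the single-dislocation check and enters the surgical group, against the section I exclusion. Section L says that a dislocation before surgery would put the patient in the non-surgical class. On either reading that patient does not belong in the surgical group.

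**Working it through.** **Inputs (section G).** Two-year risks of 25% (non-surgical) and 20% (surgical), two-sided alpha 5%, 90% power, 10% loss, equal groups, N = 3065, 656 events.

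**The plan's own figures.**
- HR = ln(0.80)/ln(0.75) = 0.7757, stated as 0.78.
- Events needed: 652 (Schoenfeld) or 659 (Freedman), against 656 stated.
- With hazard λ = −ln(1 − risk) and loss hazard e = −ln(0.90) = 0.1054, the probability of an observed event is λ/(λ+e) × [1 − exp(−(λ+e))]. This gives 0.2379 and 0.1902, mean 0.2140. Then 656/0.2140 = 3065.
- Power = Φ(½√656 × |ln 0.7757| − 1.96) = 0.90.

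The sample size reproduces. It treats every re-dislocation as observed, apart from loss to follow-up.

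**Equal under-capture.** Let s be the share of patients with a re-dislocation whose event reaches a CPRD code. The documents give no value, so s is an assumed range. Observed risks are 0.25s and 0.20s, and N stays at 3065.

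Example, s = 0.80: risks 0.20 and 0.16; HR = ln(0.84)/ln(0.80) = 0.781; events 525; power = Φ(½√525 × 0.2467 − 1.96) = Φ(0.87) = 0.81.

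| s | HR | Events | Power | N for 90% power |
|---|---|---|---|---|
| 1.0 | 0.776 | 656 | 0.90 | 3047 |
| 0.9 | 0.779 | 590 | 0.86 | 3485 |
| 0.8 | 0.781 | 525 | 0.81 | 4038 |
| 0.7 | 0.784 | 459 | 0.74 | 4743 |
| 0.6 | 0.787 | 393 | 0.66 | 5690 |

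(The last column uses the Schoenfeld event count, hence 3047 and not 3065 in the first row.)

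**Unequal capture, for illustration only.**
- 80% control, 90% surgical: risks 0.20 and 0.18; HR = ln(0.82)/ln(0.80) = 0.889; power 0.28.
- 90% control, 80% surgical: risks 0.225 and 0.16; HR = ln(0.84)/ln(0.775) = 0.684.
- No true effect (25% in both arms): the same two cases give ln(0.775)/ln(0.80) = 1.14 and ln(0.80)/ln(0.775) = 0.88.

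**Can the validation criterion detect the problem?** Positive predictive value is true positives/(true positives + false positives). Missed events are false negatives and do not enter it. A code set could pass at 75% or more with any level of missed recurrences.

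**The case against.** The strongest reply is that the protocol already treats recurrence coding as its main uncertainty. Poor recurrent-dislocation coding stops the study, item 6c asks about uncoded recurrences, section F says the code lists will be validated and informed by Work Package 1, and an updated analysis plan goes to the funder before Work Package 2. This stands in part: the authors know of the risk and have a stage at which to act on it. It does not settle the matter. No threshold is attached to missed recurrences. Section F does plan to estimate sensitivity of the diagnosis by searching alternative GP diagnosis codes, but sets no threshold and stays within the GP record. Item 6c is reached only when there is no further code, and sees only what the practice's notes hold. Nothing in the plan adds a hospital source.

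Two stronger readings are tempting and should not be made.

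- A reader might infer that GP coding differs between arms and so biases the hazard ratio. No section says so. If re-dislocations in both arms go to hospital, both depend on the same route from hospital to GP, and Appendix G lists hospital as well as community physiotherapy, so conservative care is not shown to be GP-led.
- A reader might infer that section N ("Although no missing is expected for the study exposure or outcomes") contradicts item 6c. It does not. Section N concerns missing values and their imputation; an uncoded event is recorded as absent, which is misclassification.

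A further fair point is that hospital data may recover only some events. Section F mentions inpatient and outpatient data for costing and Appendix F describes admission episodes; nothing shows that the extract holds A+E attendances.

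**Conclusion.** The concern holds as a gap in ascertainment that should be closed. Both the primary endpoint and the single-dislocation check depend on CPRD codes alone, and the statement that all events and outcomes use Read and OPCS codes is not delivered for dislocations by the lists in Appendices C and D.

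If capture is equal in both arms, the expected cost is power and not bias: HR 0.78 to 0.79, power about 0.81 at 80% capture and 0.66 at 60%. A 10-point difference between arms would move the HR to about 0.68 or 0.89, but neither a difference nor its direction is supported by the documents. All capture values are assumptions. The calculation also takes the section G risks as true and treats an uncoded patient as event-free. The number of patients wrongly admitted to the surgical group cannot be estimated from the protocol.

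**What to change.** In the code-list revision before Work Package 2:

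1. Add to the HES list closed reduction of shoulder dislocation, and a shoulder-dislocation diagnosis on an unplanned admission.
2. Define a dislocation as a CPRD or HES record. Pre-specify a window within which records count as one episode, so that a hospital record and a later GP entry are not counted twice. Exclude the elective stabilisation admission itself.
3. Apply the same combined rule to the first-dislocation definition and its two-year washout, to the check for further dislocations before surgery, and to the outcome.
4. Report the CPRD-only result as a sensitivity analysis.

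The cost is a longer code list on data already being linked, a rule for merging records, and one extra run. The limitation is that, unless the extract includes A+E attendances, capture improves but stays incomplete, and the report should say so. Section N needs no change on this ground.

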Study Design: This study design is in two phases requiring 2 Work Packages (WP). WP1 will test the internal and external validity of CPRD coding in identifying patients with T ASD and any treatments. 100 random sets of CPRD notes of patients aged 16-35 years with first time T ASD will be analysed for validity of coding and completeness of relevant data. Age-gender prevalence rates of the data set will also be compared to published age-gender prevalence rates from other settings.

WP2 is the main study and is a population based propensity score-matched cohort study using the CPRD and HES datasets. This is one of the best designs and approaches now available in dealing with confounding by indication present in observational data. The propensity scoring approach will ensure that each patient receiving surgery for T ASD is matched to a comparable non-surgical control.

F. Study Design

We will use CPRD and the Hospital Episodes Statistics (HES) as our data sources. However, with no previous reports on the validity of shoulder dislocation coding in CPRD, we are conducting the study in two phases (Work Packages 1 and 2). Before conducting the population based cohort study (WP2), we plan to validate these cohorts through WP1. A validation algorithm is included in appendix H. We plan a CPRD internal validation notes review and we will also test the sensitivity and specificity of these codes in CPRD. An external validation of the age/gender prevalence rates in CPRD for this condition will also be performed. There will then a 2 month stop gap during which a report and updated analysis plan will be submitted to the HTA justifying progression to WP2.

This project was funded by the National Institute for Health Research Health Technology Assessment (project number 14/160/01).

The views and opinions expressed therein are those of the authors and do not necessarily reflect those of the HTA, NIHR, NHS or the Department of Health.

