The ***Intervention group*** will be patients in CPRD with first time T ASD who underwent shoulder stabilisation surgery after their first dislocation (early surgical repair in this NHS context will mean 'a decision to treat surgically after the first T ASD' and receiving surgery within 6 months). This means linking HES data to CPRD data in such a way that a HES surgical OPCS 4.7 code is seen to occur after a single first dislocation code in CPRD (without further dislocation codes) before that surgical date. The timelines between first dislocation codes and OPCS 4.7 codes will be recorded. The ***Control group***. While the most desirable control group would be physiotherapy, it is possible that WP1 will reveal that free text notes and referral codes on physiotherapy will be lacking and not reliable. If this is the case then conservative care will be defined as 'non surgical intervention' with no linked OPCS 4.7 surgical shoulder codes producing a control cohort of patients whose first time shoulder dislocation has been treated non-operatively. If however free text entries and referral codes for physiotherapy are reliably present in CPRD then conservative care will be physiotherapy identified by physiotherapy referral codes after a first time T ASD code. Any subsequent dislocation codes or OPCS 4.7 surgery code will be recorded.

K. Exposures, Outcomes and Covariates

As part of this application, we have performed a consensus survey of specialist shoulder surgeons and shoulder physiotherapists who are all members of the British Elbow and Shoulder Society. Saturation point and a list of predictors was reached rapidly and this list is tabulated in Appendix E and highlights the risk factors (and covariates) deemed most important. It is unlikely that all of these will be available from routinely collected national datasets but our study design will allow us to confirm through WP1 those factors that are reliably collected and that can be used for full analysis in WP2.

L. Data/ Statistical analysis

The association of surgical versus non-surgical intervention on subsequent re-dislocation within 2-years. The primary outcome of interest is the time from a first time traumatic anterior dislocation to subsequent re-dislocation within 2-years. The exposure of interest is whether or not a patient received shoulder surgery. In randomized controlled trials each person has

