3.	Do MRI or X-ray imaging reports confirm a diagnosis of traumatic dislocation by mentioning the presence of Hill Sachs, Bankart lesion, labral tear, labral detachment, dislocation, relocation, bony Bankart?	(If YES go to Q5)	(If NO go to Q4)

This project was funded by the National Institute for Health Research Health Technology Assessment (project number 14/160/01).

The views and opinions expressed therein are those of the authors and do not necessarily reflect those of the HTA, NIHR, NHS or the Department of Health.

4.	Do Hospital letters from specialists or physiotherapists confirm traumatic instability or traumatic shoulder dislocation?	(If YES go to Q5)	(If NO go to Q8)
5.	Is there any record of a dislocation prior to the CPRD first registration date at your practice?	(If YES go to Q6)	(If NO go to Q6)
6.	Are there any further dislocation codes in the record during the 2 years after the first dislocation code?	(If YES go to Q6b)	(If NO go to Q6c)
6b.	If YES is it clear (for each one) that this is a further dislocation episode rather than simply a review of the problem?	(If YES go to Q7)	(If NO go to Q7)
6c.	If NO, have there been any further dislocations recorded during the following 2 years that are not electronically coded?	(If YES go to Q7)	(If NO go to Q7)
7.	Are there any physiotherapy treatment codes for 2 years after the first dislocation code?	(If YES go to Q7b)	(If NO go to Q7c)
7b.	If YES is it clear that this physio code indicates the patient received physiotherapy for their shoulder?	(If YES go to Q8)	(If NO go to Q8)
7c.	If NO, is there any documentation that the patient has received physiotherapy for their shoulder without a code being entered?	(If YES go to Q8)	(If NO go to Q8)
8.	If your specific responses to this questionnaire indicate that this patient has not had a traumatic shoulder dislocation but your reading of the notes or your knowledge of the patient suggest they might have please tick the YES box, otherwise tick the NO box.	The end – thank you	The end – thank you

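### Work Package 1 is said to validate treatment coding, but its questionnaire has no item on shoulder surgery, the exposure that defines both groups

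*Protocol*

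**What the plan says.** **Promised scope.** The Technical Summary and Section C describe WP1 as validating the coding of shoulder dislocation and of treatments in CPRD. Section E repeats this: "WP1 will test the internal and external validity of CPRD coding in identifying patients with T ASD and any treatments". Section F (Main study) says that events and outcomes in WP2 will come from READ and OPCS 4.7 lists, and adds: "They will be further validated and informed by WP1".

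**The exposure.** Section L: "The exposure of interest is whether or not a patient received shoulder surgery". Sections F and J define the intervention group by linkage, such that "a HES surgical OPCS 4.7 code is seen to occur after a single first dislocation code in CPRD", with surgery within 6 months and no further dislocation code before it. If physiotherapy data prove unreliable, controls are patients with no linked surgical code.

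**The instrument.** Version 2 replaced the review of 100 sets of notes with the GP questionnaire in Appendix I. Its only treatment question is Q7, "Are there any physiotherapy treatment codes for 2 years after the first dislocation code", with follow-ups 7b and 7c.

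**The surgical list.** Appendix C gives the OPCS codes, supplied by an expert adviser to the national classifications service. Codes that do not define a site need Z81.3 or Z81.4. The italicised codes, usually used for other joints, "will therefore need to be included in the analysis during linkage to CPRD shoulder dislocation codes".

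**The concern.** The protocol claims that WP1 validates treatment coding, but the instrument it now uses measures one treatment, physiotherapy, and not the one under study. Surgery yes or no defines the groups, is the dependent variable of the propensity model, and carries the hazard ratio. Section N expects no missing exposure data, and no step described in the protocol compares a surgery code with a patient's record.

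Some operations counted as stabilisation may be something else, and some stabilisations may be absent from the linked record. If such errors are unrelated to recurrence risk, they pull the hazard ratio towards 1. The stop/go criterion would not reveal them, because it concerns dislocation coding.

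**Working it through.** **1. Scope against instrument.** The questionnaire items, in order:

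- Q1 and Q2: dislocation, instability or injury documented
- Q3: imaging
- Q4: hospital letters confirming traumatic instability or dislocation
- Q5: earlier dislocation
- Q6, 6b, 6c: further dislocations, coded and uncoded
- Q7, 7b, 7c: physiotherapy, coded and uncoded
- Q8: overall judgement on traumatic dislocation

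Items on physiotherapy: 3. Items on surgery: 0. The three aims in the covering letter concern dislocation and recurrence. Section F's account of what is assessed names dislocation, cause, later events and physiotherapy, but not surgery. Its red-light rule and 75% PPV threshold refer to dislocation coding.

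**2. The plan's own sample size (Section G).** Inputs: 25% against 20% at 2 years, two-sided 5%, 90% power, equal groups, 10% loss.

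- HR = ln(0.80)/ln(0.75) = 0.7757, stated as 0.78.
- Events needed: 652 (Schoenfeld) or 659 (Freedman). The stated 656 lies between them.
- With loss as an exponential competing process over 2 years, the mean event probability is 0.2140, and 656/0.2140 = 3065, as stated.
- Power at 656 events = Φ(|ln HR| × √656/2 − 1.96) = 90%.

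The plan's figures reproduce and are not in dispute.

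**3. Illustration of exposure error.** Let a be the share of the surgical group without a stabilisation and b the share of controls with one. Both are assumed, and error is taken to be unrelated to recurrence risk. Then S = 0.20(1 − a) + 0.25a, C = 0.25(1 − b) + 0.20b, and HR = ln(1 − S)/ln(1 − C). Power uses the formula above, for an unpaired log-rank test with events held at 656.

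| a | b | S | C | HR | Power |
|---|---|---|---|---|---|
| 0 | 0 | 0.2000 | 0.2500 | 0.776 | 90% |
| 0.10 | 0 | 0.2050 | 0.2500 | 0.798 | 83% |
| 0.10 | 0.03 | 0.2050 | 0.2485 | 0.803 | 80% |
| 0.25 | 0 | 0.2125 | 0.2500 | 0.830 | 66% |
| 0.20 | 0.10 | 0.2100 | 0.2450 | 0.839 | 61% |

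**4. What a surgery item could show.** Assume 100 forms, the stated 80% return and the 35% operated in Appendix B: 100 × 0.80 × 0.35 = 28 operated patients. Appendix F puts HES linkage at over 60% of CPRD; at 60%, 28 × 0.60 ≈ 17 would have OPCS data. An observed PPV of 21/28 = 75% has an exact 95% interval of 55% to 89%.

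**The case against.** Several points on the other side stand.

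- Section E speaks of CPRD coding, whereas the exposure is a HES code. The promise that covers OPCS rests on one general sentence in Section F. That sentence does name both lists, and Appendix A gives CPRD surgery codes that fall within Section E's wording, so the mismatch remains.
- A reader might infer that procedures on other joints enter the surgical group unchecked. Appendix C does not support that: it requires a shoulder site code where the procedure code has none, the list came from a classification expert, and Sections F and J require the code to follow a single dislocation code within 6 months. These rules narrow wrong-joint error. They do not show that the operation was a stabilisation (the list includes W84.9, an unspecified endoscopic operation), nor that no operation was missed.
- A reader might infer that nothing else in WP1 touches surgery and that progression is automatic. Section K says WP1 will confirm which Appendix E factors are reliably collected, and these include operation type and time to surgery. Section F requires a report to the funder justifying progression. The Appendix H algorithm is not visible. However, the questionnaire is said to follow that algorithm, and no item in it collects surgical data.
- A GP form can only partly validate HES codes, and linkage comes after a positive WP1. This limits the remedy, but Q4 already relies on hospital letters, so asking for an operation and its date is feasible.

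**Conclusion.** The concern holds as a mismatch between what WP1 is said to validate and what Appendix I collects: as written, WP1 gives no record-level check of the main exposure. A later analysis plan could not recover answers that the forms never asked for.

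The documents do not support the stronger inference that surgery coding is poor or that the study is underpowered. They give no error rates. The falls in power to 80% or 61% are illustrations that rest on assumed rates, on misclassification unrelated to recurrence risk, and on events fixed at the required 656. The point merits correction before the forms go out; it is not a reason to stop.

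**What to change.** Add one item to Appendix I, between the physiotherapy questions and Q8, for all cases confirmed as traumatic dislocation: did the patient have an operation to stabilise this shoulder after the first dislocation? If so, ask for the date and procedure from the hospital letter; if not, ask the GP to confirm that none is documented.

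- In the WP1 report, compare the answers with the Appendix A READ codes.
- At the start of WP2, for linked patients, compare them with the Appendix C OPCS codes.
- In both, report overall PPV and missed operations with confidence intervals.
- Do not drop individual codes because the sample fails to confirm them: Appendix C has about 40 entries, and at most about 28 operated patients cannot test each one. Instead, run a WP2 sensitivity analysis that excludes the italicised codes.

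If the item is not added, amend the Technical Summary and Sections C, E and F to say that WP1 validates dislocation and physiotherapy coding only.

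The cost is one questionnaire item, two short tables and one sensitivity analysis. The limitation is precision: about 28 operated patients, fewer with linkage, can reveal only gross error.
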